Amendment 3	Sept 6, 2018	
1. Primary analysis changed to descriptive statistics, as defined in the protocol.2. Imputation rule changed for primary, secondary [REDACTED] [REDACTED] analyses by not excluding data after the use of the treatments prohibiting further use of investigational ranibizumab (protocol Table 5-2).3. AEs presented by switch/no switch removed following the amendment of the protocol.4. Additional analyses added to the interim analyses II in Sections 2.14 and 2.15.5. Analysis of recurrence of ROP up to Week 52 removed, as it's not applicable.6. Output of demographics and baseline characteristics at core baseline included in IA2 in Section 2.157. Definition of absence of ocular structural abnormalities updated in Section 2.8.18. Interim analysis II updated in Section 2.15 
[REDACTED]

Version	Date	Changes
Amendment 4	December 16, 2019	1. Definition on the composite and individual components of ocular structural abnormality updated in Section 2.8.1, to align with the protocol.
Amendment 5	May 24, 2022	
1. Align section numbers in Table 1.12. Update definition of study day relative to Core/Extension baseline.3. Update mapping rules for end of study visit4. Update definitions of better-seeing eye, worse-seeing eye, best eye, worst eye, best vision of the Low Visual Acuity Testing5. Added several sensitivity analyses for the primary endpoint6. Added analyses for the Low Visual Acuity Testing7. Added outputs for AEs that start prior to / on or after the Extension baseline8. Added reference SAS code for unstratified ANOVA

Table of contents

Table of contents	4
List of abbreviations	6
1 Introduction	7
1.1 Study design.....	7
1.2 Study objectives and endpoints	8
1.3 Cut-off dates	12
2 Statistical methods.....	12
2.1 Changes to the planned analyses in the protocol	12
2.2 Data analysis general information	13
2.2.1 General definitions	13
2.2.2 Data for permanent study treatment discontinuation	17
2.3 Analysis sets	17
2.4 Patient disposition, demographics and other baseline characteristics	17
2.4.1 Patient disposition	19
2.4.2 Baseline and demographic characteristics	19
2.5 Treatments (study treatment, rescue medication, concomitant therapies, compliance).....	21
2.5.1 Study treatment / compliance.....	21
2.5.2 Prior and concomitant medications	21
2.5.3 Surgical and medical procedure	23
2.6 Analysis of the primary objective.....	23
2.6.1 Primary endpoint.....	23

1.1 Study design

This is a multicenter open-label Extension study ([Figure 1-1](#)). Patients who have successfully completed the 24-week Core study (CRFB002H2301) are eligible for entry into the study. Visit 201/ baseline visit of the Extension study can occur on the same day as the last visit in the CRFB002H2301 study.

At Visit 201 (Extension baseline), the investigator or his/her delegate will contact the IRT after confirming the patient fulfills all the inclusion/exclusion criteria. Sample size estimation or formal power calculation was not done for this study. The number of patients is the actual enrollment in the Extension study (Section 4 of study protocol).

Treatment with study ranibizumab (either as re-treatment after ranibizumab has already been injected or as switch ranibizumab treatment from study laser therapy administered in the Core study) will be permitted for eligible eyes up to and including the study visit V203 (week 40 from the baseline visit in the Core study (CRFB002H2301) (equal to week 16 from the baseline visit in Extension study, when the baseline visit in Extension study coincides with the week 24 visit in the Core study) [Epoch 1]). During Epoch 1, the investigator or his/her delegate will contact the IRT upon decision to administer study treatment. IRT will specify a unique medication number for the package of study drug to be dispensed to the patient. The remainder of the Extension study (from the study visit V203, to patients' 5th birthday visit) [Epoch 2] is observational.

[figure not shown]
Assessment visits will be performed regularly throughout Epoch 1 and Epoch 2, with the last study visit to be as close as possible to the patient's fifth birthday. The assessments related to the primary objective will be performed at the study visit V399, corresponding to the approximate time of the patient's fifth birthday.

Two interim analyses are planned for the study. Additional interim analyses may be conducted on safety or efficacy data as required.

The first interim analysis will be conducted to comply with the plan for specific follow-up set out in the Pediatric Investigational Plan (PIP) with the EMA and to support the inclusion of information related to the treatment of ROP in the Lucentis product information. This will be performed when the last patient has completed the last visit in the Core study or when at least half of the patients who were enrolled in the Core study have completed the visit which corresponds to the visit occurring 40 weeks after the first study treatment (in the Core study), whichever is the latest.

The second interim analysis will be performed when the last patient has completed the visit which corresponds to the patient's 2 years' corrected age. A patient's corrected age is its chronological age corrected for its prematurity, i.e. calculated by subtracting the number of weeks of prematurity from the chronological age.

Figure 1-1 Study design

1.2 Study objectives and endpoints

[figure not shown]
All study objectives will be assessed by initial study treatment received at baseline of the Core study CRFB002H2301. The objectives, along with its endpoints and time point for analyses are presented in [Table 1-1](#).

[figure not shown]
Table 1-1 Study objectives and endpoints

OBJECTIVE	Endpoint Title, Description and Reporting Time frame for analysis and Unit of measure
Primary	
To evaluate the visual function of patients, by assessing the visual acuity in the better-seeing eye at the patient's fifth birthday ^{a,e}	Title: visual acuity in the better-seeing eye at the patient's fifth birthday Unit of measure: visual acuity score (Lea symbols optotypes) Time frame: at the patient's fifth birthday ^e
Secondary	
To evaluate the safety outcomes by analyzing the type, frequency and severity of ocular and non-ocular Adverse Events ^b	Title: ocular and non-ocular Adverse Events Unit of measure: number and percentage of patients having e.g. any AE; number of hospitalization/ prolongation of hospitalization due to SAE Time frame: from the first study treatment in the Core study up to V203 (Week 40), V302 (the patient's 2 years' corrected age) and V399 (the patient's fifth birthday) in the Extension study

OBJECTIVE	Endpoint Title, Description and Reporting Time frame for analysis and Unit of measure
To evaluate the visual function by assessing the visual acuity in the worse-seeing eye at the patient's fifth birthday ^a	
Title: visual acuity in the worse-seeing eye at the patient's fifth birthday
 
Unit of measure: visual acuity score (Lea symbols optotypes)
 
Time frame: at the patient's fifth birthday

To evaluate the absence of active ROP at 40 weeks and 52 weeks post baseline visit in the Core study	
Title: absence of active ROP
 
Unit of measure: number and percentage of patients
 
Time frame: at V203 and V301 (40 weeks and 52 weeks post baseline visit in the Core study)

To evaluate the absence of ocular structural abnormalities at or before 40 weeks post baseline visit in the Core study, at the patient's 2 years' corrected age and fifth birthday	
Title: absence of all ocular structural abnormalities as listed in Section 2.8.1
 
Unit of measure: number and percentage of patients
 
Time frame: at or before V203 (Week 40) in the Core/ Extension study, at or before V302 (the patient's 2 years' corrected age), at or before V399 (the patient's fifth birthday)
 
Title: absence of each ocular structural abnormality as listed in Section 2.8.1 considered individually
 
Unit of measure: number and percentage of patients
 
Time frame: at or before week 40, at or before patient's 2 years' corrected age, at or before patient's fifth birthday

To evaluate the recurrence of ROP up to 40 weeks post baseline visit in the Core study	
Title: recurrence of ROP
 
Unit of measure: number and percentage of patients with recurrence of ROP
 
Description: Recurrence of ROP is defined as ROP receiving any intervention after the 1st study treatment in the Core study^d.
 
Time frame: up to 40 weeks postbaseline visit in the Core study

To assess the number of ranibizumab injections received in the treatment of patients with ROP up to and including 40 weeks post baseline visit in the Core study	
Title: number of ranibizumab injections
 
Unit of measure: number of ranibizumab injections
 
Description: as per title
 
Time frame: up to and including 40 weeks post baseline visit in the Core study

OBJECTIVE	Endpoint Title, Description and Reporting Time frame for analysis and Unit of measure
To evaluate the refraction in each eye at the patient's 2 years' corrected age and fifth birthday ^a	
Title: refraction in each eye Unit of measure: diopters Time frame: at patient's 2 years' corrected age, patient's fifth birthday

To evaluate the physical development at the patient's 2 years' corrected age and fifth birthday ^b	
Title: standing/sitting height, leg length, weight Unit of measure: centimeter, gram (as appropriate) leg length will be derived from standing/sitting height difference Time frame: at the patient's 2 years' corrected age, at the patient's fifth birthday
 
Title: head circumference Unit of measure: centimeter Time frame: at the patient's 2 years' corrected age

To evaluate the health status at the patient's 2 years' corrected age and fifth birthday ^{b,c}	
Title: respiratory function^b Unit of measure: number and percentage of patients with oxygen supplementation; with presence of wheezing symptoms
 
Title: hearing function^c Unit of measure: number and percentage of patients with presence of hearing impairment
 
Title: duration of hospitalization after first hospital discharge home; weight at first hospital discharge home Unit of measure: days/months as appropriate; gram
 
Time frame: at the patient's 2 years' corrected age, at the patient's fifth birthday

OBJECTIVE	Endpoint Title, Description and Reporting Time frame for analysis and Unit of measure
	

- a - Variable corresponding to “ocular effects” in the plan for specific follow-up in the Pediatric Investigation Plan (EMA)
- b - Variable corresponding to “clinical outcomes” in the plan for specific follow-up in the Pediatric Investigation Plan (EMA)
- c - Variable corresponding to “neurodevelopmental outcomes” in the plan for specific follow-up in the Pediatric Investigation Plan (EMA)
- d - Supplementary laser treatments (as per CRFB002H2301 study protocol) are considered part of the complete laser treatment
- e - At the visit as close as possible to the patient’s fifth birthday

1.3 Cut-off dates

Interim Analysis I: only subjects who have completed Week 40 visit prior to or on December 31, 2017 will be included in Interim Analysis I. For all domains with visit numbers (e.g., DM, DS, ZX, EX), Week 40 visit number will be used for cut-off. For event data without visit number (e.g., AE), December 31, 2017 will be used as the cut-off date.

Interim Analysis II: all subjects from the extension safety set will be included in Interim Analysis II, with a cut-off date defined as the date when the last patient has completed the 2 years’ corrected age visit. For all domains with visit numbers (e.g., DM, DS, ZX, EX), the 2 years’ corrected age visit number will be used for cut-off. For event data without visit number (e.g., AE), all data up to the cut-off date will be reported.

2 Statistical methods

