2.3 Analysis sets

The Extension Safety Set for this study is defined as the subset of the patients from the Safety Set of the Core study who enter this Extension study and comprises data from both the Core and Extension studies.

All analyses will be carried out on the Extension Safety Set and displayed by the initial study treatment received at the baseline of the Core study unless otherwise specified.

[Table 4-1](#) shows the protocol deviations leading to data exclusion from the analysis data set.

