2.4.1 Patient disposition

All disposition tables will be based on the Extension safety set. Subject disposition data is collected in specific eCRF disposition pages based on the epochs (time intervals in the course of the study) as defined in the protocol; reporting of disposition data will be presented by epoch.

The Extension study period starts from Extension baseline and includes 2 epochs: post-treatment follow-up 1 and post-treatment follow-up 2.

The number and proportion of patients who completed each epoch and who discontinued the study prior to completion of the epoch will be presented. Also the number and proportion of the primary reason for not completing each epoch will be presented.

The primary reason for premature study discontinuation and permanent study treatment discontinuation will be displayed by actual treatment and overall for this Extension study.

Baseline-Failure Subjects are patients with informed consent obtained from their parent(s) or legal guardian(s) but who were discontinued at the baseline visit because they did not meet all inclusion/exclusion criteria. The number of these patients and their reasons for inclusion/exclusion failure will be summarized.

The number of patients with CSR reportable PDs according to the applicable SOP will be presented for this Extension study. The results will be grouped using the broad categories defined in the applicable SOP, which currently are:

- Eligibility: Patients who entered the trial even though they did not satisfy the entry criteria
- Withdrawal: Patients who developed withdrawal criteria during the trial, but were not withdrawn
- Study Drug: Patients who received the wrong treatment or incorrect dose
- Concomitant Medication: Patients who received an prohibited concomitant medication
- Other reportable protocol deviation

The reasons for exclusion from efficacy or safety analysis will be listed.

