2.15 Interim analysis

Two interim analyses will be performed by the Novartis CTT.

Interim Analysis I:

The first interim analysis will be performed when the last patient has completed the last visit in Core study or when at least half of the patients enrolled in the Core study have completed the visit corresponding to 40 weeks after the first study treatment (in the Core study), whichever is later.

The purpose of the first interim analysis is to provide some longer term data on ocular structural abnormalities. This is to comply with the plan for specific follow-up in the Pediatric Investigation Plan (EMA). At the first interim analysis, descriptive statistics will be produced as appropriate and no inferential analyses will be conducted. The variables below will be summarized.

- Epoch 1 phase subject disposition
- Subject demographics
- The absence of all ocular structural abnormalities as defined in [Section 2.8.1](#).
- The recurrence of ROP up to 40 weeks post baseline visit from the Core study
- The absence of active ROP at 40 weeks as defined in [Section 2.8.1](#)
- The number of ranibizumab injections received in the treatment of patients with ROP up to 40 weeks post baseline visit of the Core study by eye and overall
- The type, frequency, and severity of ocular and non-ocular adverse events

The above outputs will be repeated for the subgroup of Japan, to support the submission to the PMDA.

Interim analysis II:

The interim analysis II will be performed when the last patient has completed the visit which corresponds to the patient's 2 years' corrected age.

The purpose of the second interim analysis is to evaluate the absence of all ocular structural abnormalities as defined in Interim Analysis I at the patient's 2 years' corrected age.

At the second interim analysis, the variables below will be evaluated.

The appropriate CMH test (as specified in [Section 2.6.2](#)) with ROP Zone at Core baseline as stratification factor will be used to analyze secondary binary efficacy variables ([Section 2.8.1](#)) at interim analysis II. p-values and 95% confidence intervals will be provided. No adjustment for multiplicity will be conducted. For other variables, descriptive statistics will be provided by treatment arm.

Binary variables:

- The absence of all ocular structural abnormalities (as in [Section 2.8.1](#))

Other variables:

- The absence of each of the ocular structural abnormalities defined in [Section 2.8.1](#)

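### Interim Analysis I admits only Week 40 completers, so Extension children who died or withdrew between entry and Week 40 are missing from its disposition and safety tables

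*SAP*

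**What the plan says.** Section 1.3 sets the population of the first interim: "only subjects who have completed Week 40 visit prior to or on December 31, 2017 will be included in Interim Analysis I". It makes no exception for children who died or withdrew earlier. For adverse events it adds: "For event data without visit number (e.g., AE), December 31, 2017 will be used as the cut-off date".

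Section 2.15 lists the outputs of this interim. They include:
- "Epoch 1 phase subject disposition"
- "The recurrence of ROP up to 40 weeks post baseline visit from the Core study"
- "The type, frequency, and severity of ocular and non-ocular adverse events"
- absence of all ocular structural abnormalities, absence of active ROP at 40 weeks, and the number of ranibizumab injections up to 40 weeks.

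Other sections point to a different population. Section 2.4.1 says: "All disposition tables will be based on the Extension safety set". It asks for the number who completed and who discontinued each epoch, with the primary reason. Section 2.3 gives the default: "All analyses will be carried out on the Extension Safety Set", unless otherwise specified. For the second interim, section 1.3 itself says that "all subjects from the extension safety set will be included in Interim Analysis II".

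**The concern.** Membership of the first interim depends on something that happens after entry, namely completing the Week 40 visit. Limiting an interim to children for whom Week 40 has fallen due is ordinary administrative practice. This rule goes further and removes children who were due but did not get there.

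Section 1.1 says that this interim serves the paediatric follow-up plan and supports the product information. If children leave because they died or fared badly, or leave more often in one arm, a reader of this report could not see it: the children are gone from both numerator and denominator.

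**Working it through.** The SAP gives no sample size, dropout rate or event count on this point, so there is no stated figure to reproduce. The check compares sections, followed by a labelled illustration.

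**1. Who is excluded.** Section 1.1 opens the Extension to children who completed the 24-week Core study. With day 1 as the first treatment, Week 24 is day 24 × 7 + 1 = 169 and Week 40 is day 40 × 7 + 1 = 281. The rule therefore acts on losses between about day 169 (later if there was a gap before Extension entry) and day 281, that is (281 − 169)/7 = 16 weeks.

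**2. Whether the visit mapping brings them back.** Table 2-2 in section 2.2.1.2 allocates a premature withdrawal visit on days 254–323 to Week 40. In weeks this is (254 − 1)/7 = 36.1 to (323 − 1)/7 = 46.0. A withdrawal visit on days 197–253 goes to Week 32. If a mapped visit counts as completed, the exposed interval for withdrawals with a visit shrinks to about days 169–253, or (253 − 169)/7 = 12 weeks. Section 1.3 does not say whether it counts. A death without a visit is not brought back in either case.

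**3. Disposition.** Section 1.1 ends Epoch 1 at V203, Week 40. Entry to the interim and completion of Epoch 1 are thus nearly the same condition. The table shows about 100% completion and almost no reasons for discontinuation, whatever happened, so it cannot deliver what section 2.4.1 asks for.

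**4. Events already recorded.** Three outputs do not need a Week 40 visit to be positive:
- Adverse events are dated. The 31 December 2017 cut-off decides which events count among admitted children; it does not admit anyone.
- Recurrence (section 2.8.1) is any study intervention after the first Core treatment.
- A structural abnormality (section 2.8.1) counts as present if seen at any visit up to the time point. A child with one recorded at Week 32 who then leaves has a known outcome and is still dropped.

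Under section 2.3 the Extension Safety Set holds Core and Extension data together, so excluding a child also removes that child's Core-period data.

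**5. Illustration (all inputs assumed).** Let d be the share of entrants lost before Week 40 and r the recurrence proportion:

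rate in all entrants = (1 − d) × r(completers) + d × r(leavers)

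Take r(completers) = 15%, which is what the interim would report.

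| d | r(leavers) | All entrants | Reported |
|---|---|---|---|
| 2% | 45% | 0.98 × 15% + 0.02 × 45% = 15.6% | 15% |
| 5% | 30% | 0.95 × 15% + 0.05 × 30% = 15.75% | 15% |
| 10% | 45% | 0.90 × 15% + 0.10 × 45% = 18.0% | 15% |
| 10% | 15% | 15.0% | 15% |
| 10% | 0% | 0.90 × 15% + 0.10 × 0% = 13.5% | 15% |

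The last row is the limiting case in which leavers go too early to show a recurrence. Recurrence can move in either direction. Epoch 1 discontinuation cannot: it would be 2–10% in all entrants under these values, against about 0% under the rule.

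**The case against.** The strongest reply is that little is lost for long. Interim Analysis II takes the whole Extension Safety Set and reports again on disposition, adverse events, deaths, recurrence to Week 40 and active ROP at 40 weeks; the final analysis uses the full set too. The first interim is descriptive, tests nothing, and is meant mainly to give longer-term data on structural abnormalities, for which children with a Week 40 examination are a natural group. Section 2.3 allows another population where one is specified. The current SAP version is dated May 2022, more than four years after the interim's cut-off, so a change now means reopening a finished report.

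Most of this stands, and it limits the point to one report. It does not rescue the disposition table: section 2.4.1 has no such exception, and permission to use another population does not make that table informative.

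Two stronger readings are tempting and are not supported:
- A reader might infer that all deaths and withdrawals in the first 40 weeks are lost because of this rule. Losses before about Week 24 are outside the Extension by eligibility, and some withdrawals from about week 36 may be mapped to Week 40.
- A reader might infer that the Week 40 efficacy results are biased in a favourable direction. Early leavers have less time to show a recurrence or an abnormality, and under section 2.8.1 a leaver with complete earlier visits and no finding could count as absent. Adding them could raise or lower these percentages.

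**Conclusion.** The point holds for Interim Analysis I only. For disposition the direction is certain: non-completion of Epoch 1 is suppressed by construction, in conflict with section 2.4.1. For safety, events and deaths among the excluded children are absent from the counts. For recurrence and structural abnormalities, known outcomes are discarded, but the direction of the effect on the percentages is uncertain. The size cannot be taken from the SAP; the 2–10% loss used above is an assumption. The conclusion rests on reading the inclusion sentence literally and on at least one Extension child having been lost after entry while due for Week 40 by the cut-off. If there were none, the sentence is still wrongly framed but no number changes. It is worth correcting, and it does not threaten the final analysis.

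**What to change.** In section 1.3, replace the inclusion sentence with wording to this effect:

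> Interim Analysis I includes all Extension Safety Set patients whose scheduled Week 40 date (Core baseline plus 40 weeks) falls on or before 31 December 2017, whether or not the visit took place. Patients who died or withdrew earlier contribute data up to that point.

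Then fix the denominators by type of output:
- Disposition, adverse events, injections and recurrence: this full set.
- Active ROP at Week 40: patients assessed at that visit.
- Cumulative structural abnormalities: any recorded presence counts as presence. Early leavers with none recorded are shown separately or as missing, not as absent.

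Section 1.3 should also state whether a withdrawal visit mapped to Week 40 by Table 2-2 counts as that visit, and be reconciled with section 2.4.1.

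If the interim has already been run, it need not be reopened in full. Report by arm the number of children who were due for Week 40 by the cut-off but were excluded, with their reasons for leaving and their recorded events.

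The cost is a short amendment and some added tables. Completion and safety figures may look slightly less favourable.

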2.2.1.2 The last study visit

The last study visit is Visit 399 (including premature withdrawal). If the patient does not discontinue the study, Visit 399 will occur close to the patient's fifth birthday.

For the visual acuity at Visit 399, the study day will be allocated to the 5th birthday visit if the study day is before the 5th birthday and within 3 months of the 5th birthday, or if the study day is after the 5th birthday.

For all other variables except for the visual acuity, the study day for the premature withdrawal Visit 399 will be allocated to the nearest planned main visit if data for the nearest planned main visit does not already exist and if the study day is within the allocation windows of the planned main visit.

All applicable assessments will be captured by scheduled visit. [Table 2-2](#) shows the allocation windows of premature withdrawal visit to a scheduled main visit of H2301E1.

Table 2-2 Allocation of premature withdrawal visit

Scheduled main visit number	Scheduled visit study week/year	Scheduled visit window in days
202	Week 32	197 – 253
203	Week 40	254 – 323
301	Week 52	324 – (Start date of mother's last menstrual period – Core study baseline visit date+766)
302	2-year corrected age	(Start date of mother's last menstrual period – Core study baseline visit date+891) – (Start date of mother's last menstrual period – Core study baseline visit date+1131)
303	3-year corrected age	(Start date of mother's last menstrual period – Core study baseline visit date+1257) – (Start date of mother's last menstrual period – Core study baseline visit date+1497)
304	4 th birthday	(Start date of mother's last menstrual period + gestational age (in weeks) *7 – Core study baseline visit date +1341) – (Start date of mother's last menstrual period + gestational age (in weeks) *7 – Core study baseline visit date +1581)
	5 th birthday	For visual acuity: (Start date of mother's last menstrual period + gestational age (in weeks) *7 – Core study baseline visit date +1736) – End of study For variables other than visual acuity: (Start date of mother's last menstrual period + gestational age (in weeks) *7 – Core study baseline visit date +1706) – (Start date of mother's last menstrual period + gestational age (in weeks) *7 – Core study baseline visit date +1946)

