- Posterior retinal fold involving the macula
- Retinal detachment involving the macula

The absence is defined as the absence of the above individual components at all visits prior to and at a particular time point. Therefore, at least one presence of the above individual components at any visit prior to or at that time point is considered presence of ocular structural abnormalities. If at all visits up to that time point, the entry of at least one of the individual components is missing and none of the others indicates the presence of the disease feature, the subject will be considered as having missing record for this outcome.

The absence of each ocular structural abnormality considered individually in both eyes at or before a particular time point:

- Substantial temporal retinal vessel dragging causing abnormal structural features/
macular ectopia
- Retrolental membrane obscuring the view of the posterior pole
- Posterior retinal fold involving the macula
- Retinal detachment involving the macula
- Retinal detachment not involving the macula
- Pre-retinal fibrosis
- Optic disc pallor (from Visit 301/week 52 included onwards)
- Optic disc swelling (from Visit 301/week 52 included onwards)
- Pigmentary disturbance in the macula (from Visit 301/week 52 included onwards)
- Atrophic changes in the macula_(from Visit 301/week 52 included onwards)
- Low visual acuity testing:
Descriptive statistics will be provided for the best vision of the Low Visual Acuity Testing by treatment arm for subjects who have 0 or missing ETDRS letter scores at the 5th birthday visit by best/worst eye.

Other efficacy variables:

Descriptive statistics with 95% Clopper-Pearson exact confidence interval will be provided for these efficacy variables by treatment arm:

- The absence of all ocular structural abnormalities (see [Section 2.15](#) for the definitions) at or before 40 weeks post baseline visit in the Core study
- The recurrence of ROP up to 40 weeks post Core baseline
- The absence of active ROP at 40 weeks post Core baseline
- The absence of each ocular structural abnormality considered individually (see [Section 2.14](#) for the definitions) at or before the patient's 2 years' corrected age and at or before the patient's fifth birthday
- At the patient's 2 years' corrected age and fifth birthday

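### At Interim Analysis II, the visit-number cut can discard withdrawal examinations made before 2 years' corrected age, because they are numbered Visit 399 and often cannot be re-allocated

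*SAP*

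**What the plan says.** - **Population.** SAP section 1.3 states that "all subjects from the extension safety set will be included in Interim Analysis II", so children who left early are in the analysis.
- **Cut.** In the same section, for domains with visit numbers, the 2-year "corrected age visit number will be used for cut-off". Data without a visit number, such as adverse events, are taken up to the cut-off date.
- **Visit number of a withdrawal.** Section 2.2.1.2: "The last study visit is Visit 399 (including premature withdrawal").
- **Re-allocation.** For everything except visual acuity, a withdrawal Visit 399 goes to the nearest main visit "if data for the nearest planned main visit does not already exist and if the study day is within the allocation windows" of that visit. In Table 2-2 the V301 window closes at LMP minus "Core study baseline visit date+766" and the V302 window runs from the same expression with +891 to +1131.
- **Endpoint.** Section 2.8.1 defines the structural outcome cumulatively: "at least one presence of the above individual components at any visit prior to or at that time point is considered presence". The outcome is missing only if, at every visit up to the time point, some component entry is missing and none shows the feature.
- **Use.** Section 2.15 gives this outcome at 2 years' corrected age as the purpose of Interim Analysis II and plans a stratified CMH test with p-values and confidence intervals.

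**The concern.** The cut works on visit numbers and the endpoint works on time. For most visits the two agree. They part for a premature withdrawal, which carries number 399 whatever its date and so lies beyond V302 even if the child left a year before the 2-year visit.

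Re-allocation is the only way back, and it has two conditions. Where either fails, no rule says what becomes of a Visit 399 examination dated before the interim cut-off. The SAP also does not say whether the cut uses the recorded or the allocated number. If it uses the recorded number, even examinations that qualify for allocation are lost.

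At stake is the classification of children in the analysis for which the interim exists. Take a child with a clean V301 whose macular detachment is first seen at a withdrawal visit some months later. Under section 2.8.1 this child has the abnormality. Under section 1.3 read literally the finding is not in the data, and because V301 was complete and clean the outcome is not missing either. The child counts as free of abnormality.

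**Working it through.** The SAP gives no figure on this point, so there is none to reproduce. The check is day arithmetic on Table 2-2.

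**1. Gap between windows (no assumption needed)**

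V301 closes at LMP+766 and V302 opens at LMP+891. The days in neither window run from LMP+767 to LMP+890: 890 − 767 + 1 = 124 days, for every child.

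**2. Days inside the V301 window but after V301 was done**

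Here the nearest main visit already has data, so allocation fails. The number of days depends on when V301 took place and on post-menstrual age at Core baseline. The SAP gives neither, so I assume:
- V301 is done on study Day 365.
- Nominal V302 is the centre of its window: (891 + 1131)/2 = LMP+1011.
- Post-menstrual age at Core baseline is 32 to 44 weeks, so LMP minus baseline is −7 × weeks.

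Worked case at 35 weeks (245 days):
- V301 window closes on Day 766 − 245 = 521.
- V302 window opens on Day 891 − 245 = 646.
- Nominal V302 is Day 1011 − 245 = 766.
- Days 366 to 521 (V301 data exist): 521 − 365 = 156.
- Days 522 to 645 (no window): 124.
- Not allocatable: 156 + 124 = 280 of 766 − 365 = 401 days, or 70%.

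| Post-menstrual age at baseline | Not allocatable | V301 to nominal V302 | Share |
|---|---|---|---|
| 32 weeks | 301 days | 422 days | 71% |
| 33 weeks | 294 days | 415 days | 71% |
| 35 weeks | 280 days | 401 days | 70% |
| 36 weeks | 273 days | 394 days | 69% |
| 40 weeks | 245 days | 366 days | 67% |
| 44 weeks | 217 days | 338 days | 64% |

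These are shares of calendar days. They equal shares of withdrawals only if withdrawals are spread evenly over the interval. They say nothing about how many children withdrew or had a new finding.

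**3. Rules side by side, for a withdrawal on Day 550 in the 35-week case, V301 complete and clean**

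| Rule | Result |
|---|---|
| 2.2.1.2: recorded number | 399 |
| 2.2.1.2 and Table 2-2: allocation | none, Day 550 lies between 521 and 646 |
| 1.3: Interim II cut at V302 | examination excluded |
| 2.8.1: presence at any visit up to the time point | examination should count |
| 2.8.1: missing-data rule with V301 complete | not missing, so classed as absent |

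The third and fourth rows contradict each other.

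**The case against.** Several points on the other side stand.

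- **The effect may be small or nil.** Only a first-ever abnormality found at an unallocated withdrawal visit changes a classification. A clean withdrawal examination changes nothing for a child with earlier complete, clean visits. The SAP gives neither the number of withdrawals nor the rate of new abnormalities.
- **The finding need not vanish from the report.** A detachment reported as an ocular adverse event is cut by date and would still appear in the adverse event tables. The structural table would then disagree with them.
- **The final analysis has no such cut.** Section 1.3 sets cut-offs for the two interims only. What stays open there is narrower: section 2.2.1.3 builds analyses up to a time point from planned main and additional assessment visits, and an unallocated Visit 399 is not clearly either.
- **Timing.** The version table dates an update of the end-of-study mapping rules to May 2022. The SAP does not say when Interim Analysis II was run or under which windows.

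A reader might also infer more than the document supports.

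- *That Interim Analysis I has the same fault.* It does not. Section 1.3 says "only subjects who have completed Week 40 visit prior to or on December 31, 2017 will be included in Interim Analysis I". A child who left before Week 40 is excluded by that restriction, and a later withdrawal properly lies beyond a Week 40 cut.
- *That withdrawn children disappear from the interim disposition table.* Section 1.3 does name DS among the domains cut by visit number. But section 2.4.1 says disposition is collected on epoch-specific pages, no visit number is given for withdrawal records, and section 2.15 uses end-of-study information for the follow-up period. This is a question for the sponsor.
- *That the treatment comparison is biased in a known direction.* A lost finding can only raise the proportion classed as free of abnormality in an arm. Nothing in the SAP says which arm would lose more.

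**Conclusion.** The concern holds for structural examinations at Interim Analysis II. Followed literally, section 1.3 excludes a withdrawal examination made before 2 years' corrected age whenever section 2.2.1.2 cannot allocate it. That contradicts the cumulative definition in section 2.8.1, and a child with earlier complete, clean visits is then misclassified as free of abnormality.

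The 124-day gap is fixed by Table 2-2 for every child. The 64% to 71% range rests on V301 at Day 365, nominal V302 at LMP+1011 and a baseline at 32 to 44 weeks. It shows that failed allocation is not a rare edge case, but it does not measure the effect on the endpoint, which cannot be known from the SAP.

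The change should be made: a stated rule gives a wrong classification in the analysis that is the interim's purpose, and the correction is cheap.

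**What to change.** 1. **Section 1.3, Interim Analysis II.** State that Visit 399 examinations are cut by date, not by visit number. An examination is kept if it is dated on or before the analysis cut-off and on or before the upper limit of the child's V302 window (LMP − Core baseline + 1131).
2. **Section 2.2.1.2.** State that, for outcomes assessed at or before a time point, a Visit 399 examination counts by its date whether or not it is allocated to a main visit. Keep Table 2-2 allocation for by-visit summaries only. This also settles the open point under section 2.2.1.3 for the final analysis.
3. **Disposition.** Ask the sponsor to confirm which visit number DS withdrawal records carry, and that withdrawals before the Interim II cut-off date are retained.

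The cost is two SAP sentences, a date condition in programming and, if the interim has been run, a rerun of the 2-year structural tables. No new data are needed. The rerun may show a few more events.
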